Outcome(s):	
Pilot Study
 
Primary outcome
 
 1. Qualitative assessment of the barriers and facilitators of the implementation of the UltraPro algorithm in a primary care practice 
Secondary outcomes
 
 1. Qualitative and quantitative assessment of the barriers and facilitators to an effective implementation of the various study procedures 
 o GPs' training curriculum: proportion of GPs who achieved the objectives of the training o Patient screening: proportion of patients who were not screened o Patient recruitment: proportion of screened patients recruited o Duration of the procedures: time spent for the different study procedures o Lung US: proportion of good quality images, proportion of correct interpretation of the images by the GP o Telephone follow-up and patients self-administered symptom diaries: proportion of patients lost to follow-up, proportion of diaries correctly completed o Patients and providers satisfaction with the study procedures 2. Adaptation of the study procedures according to the previous outcomes. 
Randomized Intervention Study
 
Primary outcome
 
 1. Proportion of patients prescribed an antibiotic in each arm by day 28 
Secondary outcomes
 
 1. Clinical outcomes 
 1. Duration of the episode: number of days during which the patient was symptomatic (defined by the daily symptom diary and phone follow-up) within 28 days 2. Duration of restricted daily activities due to a respiratory tract infection 3. Clinical failure by day 7: 
 ▪ Admission to hospital within 7 days of follow-up ▪ Death within 7 days of follow-up ▪ No amelioration or worsening of relevant symptoms (fever and/or dyspnoea) at day 7 4. Number of medical visits for the episode of LRTI within 28 days of follow-up 5. Serious adverse outcome by day 28, based on the advent of at least one of the following events: 
 ▪ Death ▪ Secondary admission to hospital for any reason ▪ Complications (persistence of pneumonia, lung abscess, lung effusion, empyema or sepsis) 6. Number of days with side effects related to antibiotics (within 28 days) 2. Consultation process 
 1. Median duration of time spent in the practice 2. Satisfaction of providers and patients 3. Economic aspects 
 1. Cost-effectiveness ratio expressed as amount of money required per 1% absolute decrease of the proportion of antibiotic prescription

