Statistical Considerations:	
The following statistical analyses are planned:
 
 • Odds ratio of antibiotic prescription between 2 groups as well as the difference in proportion of patients prescribed an antibiotic by day 28 using logistic regression corrected for variation at the GP level (generalized linear mixed effect) • Difference between the mean number of days with restricted activities by day 7 using linear mixed effect regression • Difference between the mean number of medical consultations by day 28 using linear mixed effect regression • Odds ratio of the risk of adverse outcomes between 2 groups as well as the difference in proportion of patients with adverse outcomes and clinical failure using logistic regression corrected for variation at the GP level (generalized linear mixed effect) • Difference between the mean daily symptom scores measured in the different arms. The effects of the interventions on recovery will be studied by comparing the slopes of symptom scores over time between arms • Difference in the mean duration of total time spent in the practice using linear mixed effect regression • Difference in levels of satisfaction of providers and patients between arms • Difference in the mean cost per arm using linear mixed effect regression • Diagnostic performance of: 
 ◦ individual host biomarker(s) based on crude positive and negative likelihood ratios, and on the area under the curve of receiver operator characteristic (ROC) curves, to predict the development of a serious adverse outcome, a clinical failure, or the presence of pneumonia ◦ combined biomarkers based on sensitivity and specificity generated by classification and regression trees (CART) analyses, to predict the development of a serious adverse outcome, a clinical failure, or the presence of pneumonia
GCP Statement:	This study will be conducted in compliance with the protocol, the current version of the Declaration of Helsinki, the ICH-GCP as well as all national legal and regulatory requirements.

ABBREVIATIONS

ARI	Acute Respiratory tract Infection
ASR	Annual Safety Report
CAP	Community Acquired Pneumonia
CEC	Competent Ethics Committee
CHUV	Centre Hospitalier Universitaire Vaudois
COPD	Chronic Obstructive Pulmonary Disease
CRP	C-reactive protein
CT	Computerized Tomography
CTU	Clinical Trials Unit
CXR	Chest X-ray
eCRF	Electronic Case Report Form
FOPH	Federal Office of Public Health

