5.2 Randomized Intervention Study

Primary outcome

Proportion of patients prescribed an antibiotic in each arm by day 28.

The following information will be collected to assess the proportion of patients prescribed an antibiotic in each arm by day 28:

- Day of the antibiotic prescription
- Antibiotic substance prescribed
- Dosage of antibiotic prescribed
- Duration of the antibiotic treatment prescribed

Secondary Outcomes

Clinical outcomes

- a. Duration of the episode: number of days during which the patient was symptomatic (defined by the daily symptom diary and telephone follow-up) within 28 days of follow-up.
- b. Duration of restricted daily activities: number of days during which the patient's daily activities (work or recreation) were restricted due to a respiratory tract infection.
- c. Clinical failure by day 7:
 - i. Admission to hospital within 7 days of follow-up
 - ii. Death within 7 days of follow-up
 - iii. No amelioration or worsening of relevant symptoms (fever and/or dyspnoea) at day 7
- d. Number of medical visits for the episode of LRTI within 28 days of enrolment.
- e. Serious adverse outcome: measured by day 28, based on the advent of at least one of the following events:
 - i. Death
 - ii. Secondary admission to hospital for any reason
 - iii. Complications (persistence of pneumonia, lung abscess, lung effusion, empyema or sepsis)
- f. Number of days with side effects related to antibiotics within 28 days of follow-up

The following information will be collected during telephone follow-up and recorded in the eCRF. It will also be obtained from the patient's diary.

Consultation process

- a. Median duration of time spent for the medical consultation, blood sampling, PCT measurement, lung US and total time spent in the practice.
- b. Quality of the ultrasound images. Agreement between GPs and experts on ultrasound images interpretation.
- c. Evaluation of the satisfaction of providers and of patients.

Economic aspects

- a. Cost / effectiveness ratio expressed as amount of money required per 1% absolute decrease of the proportion of antibiotic prescription.

Exploratory Outcomes

- a. Prevalence of different respiratory pathogens assessed by multiplex rt-PCR on nasopharyngeal swab and sputum
- b. Sensitivity and specificity of combinations of host biomarkers and gene expression signatures in identifying patients with serious adverse outcome, clinical failure or with pneumonia

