PaxGene	2.5 ml	-80°C	Transcriptomics

Table 2. Details of blood samples collected in the study

Naso-pharyngeal swabs

For future analyses, a naso-pharyngeal swab will be performed on all patients recruited in the study. A eSwab™ (Copan Diagnostics[©]) will be introduced in the nasal cavity until the naso-pharynx in one

nostrils. Swabbing will then be performed. The sample will then be conserved at -80°C using a liquid collection and transportation system.

A respiratory pathogen multiplex real time polymerase chain reaction (PCR) assay will be retrospectively performed in the laboratory of virology of Geneva University Hospital to identify the aetiological agent of the LRTI. Such an approach has been described in other studies [41].

Sputa

For future analyses, a sputum sample will be collected for all patients recruited in the study if they are able to produce it. The sample will then be conserved at -80°C.

A respiratory pathogen multiplex real time PCR assay will be retrospectively performed in the laboratory of virology of Geneva University Hospital and culture will be performed in the microbiology laboratory of Lausanne University Hospital to identify the aetiological agent of the LRTI.

Follow-up after initial assessment

Active surveillance

All participants will be contacted by phone at day 7 and day 28 by the study team.

At days 7 and 28, a standardized interview will be done to ensure that the patient is alive, to:

- evaluate clinical outcome (presence or recurrence of LRTIs symptoms)
- record any additional visits
- record additional antibiotic prescription
- record number of days during which daily activities (work or recreation) were restricted
- evaluate antibiotic side effects
- record secondary hospital admission
- patient satisfaction will be recorded at day 28 only

The caller will be blinded as to the arm in which the patient was included.

All participants will be asked to fill a daily diary until symptom resolution up to day 28. The diary can be filled in paper and returned by post or for participants who prefer an electronic version will be made available.

They will report each day on 6 items:

- coughing
- phlegm
- shortness of breath
- sleep disturbance
- impairment of normal daily activities
- generally feeling unwell

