11.2 Determination of Sample Size

The sample size was calculated to assess a decrease in antibiotic prescription of at least 15% between the UltraPro and the PCT arms as well as 15% between the PCT arm and usual care.

The proportion of patients receiving antibiotics with the usual care is estimated to be around 60% and to decrease to 45% using PCT and to 30% combining PCT and ultrasound. These numbers have been extrapolated from the subgroup of patients with LRTI in a study at primary care level in the Netherlands [3].

A study sample of 14 GPs and 15 patients per GP in each arm (210 patients per arm and a total of 630 patients) gives a power of 80% to detect a decrease in antibiotic prescription from 60% (usual care) to 45% (PCT), and from 45% (PCT) to 30% (UltraPro), with 5% level of significance, when adjusting for clustering at practice level (intracluster coefficient 0.06) [3]. This sample size guarantees a power of 80% to prove non-inferiority in terms of duration of activities restriction (non-inferiority margin=1 day, standard deviation=4 days) as well as of composite adverse outcome (probability in the “usual care” arm 0.05 with a non-inferiority margin of 0.02). Simulations used to determine the sample size are shown in the following figures.

[figure not shown]

Figure 4: Statistical simulations used to determine sample size

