11.4 Planned Analyses

Datasets to be analysed, analysis populations

The analysis will be performed in intention to treat (pragmatic trial). The analysis population will comprise all patients included by the randomised GPs. The primary analysis will include all patients enrolled in the study, irrespective of follow-up. Patients who are lost to follow-up will be considered as having had a clinical failure, an adverse outcome and duration of disease equal to the maximum duration measured in the other patients. Patients in whom GPs did not follow the respective algorithm recommendation and/or who did not have complete telephone follow-up will be excluded from the per-protocol analysis.

Primary Analysis

Odds ratio of antibiotic prescription between 2 groups as well as the difference in proportion of patients prescribed an antibiotic by day 28 using logistic regression corrected for variation at the GP level (generalized linear mixed effect)

Secondary Analyses

The following statistical analyses are planned:

- Difference between the mean number of days with restricted activities by day 14 using linear mixed effect regression
- Difference between the mean number of medical consultations by day 28 using linear mixed effect regression
- Odds ratio of adverse outcome between 2 groups as well as the difference in proportion of patients with adverse outcome and clinical failure using logistic regression corrected for variation at the GP level (generalized linear mixed effect)
- Difference between the mean daily symptom scores measured in the different arms. The effects of the interventions on recovery will be studied by comparing the slopes of symptom scores over time between arms
- Difference in the mean duration of total time spent in the practice using linear mixed effect regression
- Difference in levels of satisfaction of providers and of patients between arms
- Difference in the mean cost per arm using linear mixed effect regression
- Diagnostic performance of:
 - individual host biomarker(s) based on crude positive and negative likelihood ratios, and on the area under the curve of receiver operator characteristic (ROC) curves, to predict the development of a life-threatening disease, clinical failure, or the presence of pneumonia (using a clinical diagnosis).

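### Days with restricted activities, an outcome powered for non-inferiority, has a day-7 window in the synopsis, a day-14 window in 11.4 and none in 5.2 or 11.2; the SD of 4 cannot fit the day-7 version, which could also hide a 1-day harm.

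*Combined protocol and SAP*

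**What the plan says.** The two current analysis lists disagree. The synopsis, under Statistical Considerations, has "Difference between the mean number of days with restricted activities by day 7 using linear mixed effect regression". Section 11.4 has "Difference between the mean number of days with restricted activities by day 14 using linear mixed effect regression".

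The outcome definitions do not settle it. Section 5.2 counts the days on which the patient's "daily activities (work or recreation) were restricted due to a respiratory tract infection", with no end point. The synopsis outcome list says only "Duration of restricted daily activities due to a respiratory tract infection". The other five clinical outcomes in 5.2 each carry a 7-day or a 28-day limit.

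Section 11.2 says the sample size guarantees 80% power for "non-inferiority in terms of duration of activities restriction (non-inferiority margin=1 day, standard deviation=4 days". It names no window. The composite adverse outcome is the only other outcome given a non-inferiority margin.

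On data collection, section 8.5 says "All participants will be contacted by phone at day 7 and day 28 by the study team", and the interviews "record number of days during which daily activities (work or recreation) were restricted". It also says "All participants will be asked to fill a daily diary until symptom resolution up to day 28". One diary item, scored 0 to 6, is impairment of normal daily activities.

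**The concern.** The alternative hypothesis in 11.1 joins fewer antibiotics to no difference in activity restriction, among other outcomes. This count is therefore part of the case that withholding antibiotics does no harm. A margin of 1 day has no fixed meaning until the counting period is fixed: 1 day out of 7 is a different tolerance from 1 day out of 28.

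Two problems follow. The SD used for sizing may not belong to the outcome that is analysed. And if the count stops early, extra restricted days that fall after the cut-off are not seen, so a harm as large as the margin can look smaller than the margin. With two current windows, either could later be cited as pre-specified.

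**Working it through.** **1. The plan's 80%.** Inputs from 11.2: 210 per arm, margin 1 day, SD 4 days, 5% significance (sidedness not stated). Assume a true difference of 0.

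- SE = 4 × √(2/210) = 0.390. Power = Φ(1/0.390 − z).
- One-sided 5%: Φ(2.562 − 1.645) = 82.0%. One-sided 2.5%: Φ(2.562 − 1.960) = 72.6%.
- With the ICC of 0.06 that 11.2 gives for antibiotic prescription, the design effect is 1 + 14 × 0.06 = 1.84 and SE = 0.530. Power is then 59.6% (one-sided 5%) or 47.2% (one-sided 2.5%).

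The stated 80% is thus roughly reproduced only at one-sided 5% without clustering. The effect of clustering on this power is a separate matter. For the present point, the calculation uses the SD of 4 and no window.

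**2. Can the SD be 4?** A variable confined to 0 to W has an SD of at most W/2.

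- W = 7: 3.5, below 4.
- W = 8 (if day 0 is also counted): 4.0, reached only if half the patients score 0 and half score 8.
- W = 14: 7.0. W = 28: 14.0.

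The SD of 4 is therefore impossible for a 0 to 7 count and possible for 14 or 28 days.

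**3. What truncation does to a true 1-day harm.** The documents give neither the mean nor the shape of the durations, so two shapes are assumed:

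- negative binomial with untruncated SD 4 in both arms, control means 3 to 7 days;
- exponential, control means 3 to 5 days. Here the SD equals the mean, so it matches the plan's 4 only when the mean is 4.

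The harmed arm has a mean 1 day longer. Let d be the difference left after truncation at W, and s₁, s₂ the truncated SDs. Then SE = √[(s₁² + s₂²) × 1.84/210] and P(declare non-inferior) = Φ((1 − d)/SE − 1.96). For the exponential, the truncated mean is m(1 − e^(−W/m)).

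Example, negative binomial, means 5 and 6, day 7: truncated means 4.12 and 4.83, d = 0.712, SDs 2.39 and 2.19, SE = 0.303. Φ(0.288/0.303 − 1.96) = Φ(−1.01) = 15.6%.

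Example, exponential, means 3 and 4, day 7: truncated means 2.71 and 3.31, d = 0.60, SDs 2.20 and 2.41, SE about 0.305, giving 26%.

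| Shape, control mean | Day 7: d, P | Day 14: d, P | Day 28: d, P |
|---|---|---|---|
| Neg. binomial, 3 | 0.87, 5.8% | 1.01, 2.4% | 1.00, 2.5% |
| Neg. binomial, 4 | 0.80, 8.9% | 1.00, 2.5% | 1.00, 2.5% |
| Neg. binomial, 5 | 0.71, 15.6% | 0.98, 2.7% | 1.00, 2.5% |
| Neg. binomial, 6 | 0.61, 30.2% | 0.97, 2.9% | 1.00, 2.5% |
| Neg. binomial, 7 | 0.49, 57.7% | 0.95, 3.2% | 1.00, 2.5% |
| Exponential, 3 | 0.60, 26% | 0.91, 4.1% | 1.00, 2.5% |
| Exponential, 4 | 0.46, 38% | 0.82, 5.5% | 0.99, 2.7% |
| Exponential, 5 | 0.36, 48% | 0.72, 7.2% | 0.96, 2.8% |

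Without clustering the day-7 figures rise, to 7.5% to 83% (negative binomial) and 44% to 74% (exponential). As an extreme case, suppose the extra days fall only on patients already restricted for 7 days or more (negative binomial, control means 4 to 6, ICC 0.06, one-sided 2.5%). A day-7 count then sees none of the harm and passes it 85% to 93% of the time. A day-14 count passes it 5% to 7% of the time.

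**The case against.** The strongest reply is that this is a secondary outcome with a wording conflict. The primary outcome is unaffected, and the other clinical outcomes in 5.2 have fixed windows. The SD of 4 is feasible for the day-14 version in the statistical section, which suggests that the synopsis line is the outlier. All of that stands, and it limits the weight of the point. It does not tell the analyst which window governs.

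A reader might also infer more than the documents support:

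- *That the impossible SD causes the masking.* It does not. Planning with too large an SD is conservative: at the ceiling of 3.5, one-sided 2.5% and no clustering, power is 83.3% against 72.6%. The masking comes from truncation alone.
- *That a day-14 count cannot be obtained because the calls are on days 7 and 28.* The diary runs daily up to day 28, and 5.2 says it also supplies this information. What is missing is a rule for which score on the 0 to 6 item makes a day restricted.
- *That day 14 is seriously biased.* Under the assumptions in the table it is close to nominal, at 2% to 7%. The serious risk lies with day 7.
- *That the error rate is 26% to 48%.* That range holds only for exponential durations. At the plan's SD of 4, the negative binomial gives 5.8% to 15.6% for the same control means.
- *That the plan will produce a false declaration.* Neither analysis list contains a non-inferiority test; both plan a difference in means. And if the outcome were deliberately defined as days restricted by day 7, a difference of about half a day would lie inside the margin. The fault would then be in pairing that window with that margin.

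**Conclusion.** The point holds. Current text gives one outcome two analysis windows, and its definition and sizing have none. The day-7 window is incompatible with the SD of 4. Both statements follow from the text and the bound W/2, with the half-and-half split under day-0 counting as the only exception.

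The size of the masking depends on assumption. With control means of 3 to 7 days, ICC 0.06 (stated for prescribing, not for this outcome) and one-sided 2.5%, a true 1-day harm passes about 6% to 58% of the time at day 7, about 2% to 7% at day 14 and about 2.5% to 3% at day 28. The direction is the same in every case examined, but no single percentage should be quoted as the trial's error rate. The conflict should be corrected; it does not undermine the primary analysis.

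**What to change.** Drop the day-7 version and state one window in the synopsis, 5.2, 11.2 and 11.4. Do this before any comparative data are seen, including the interim analysis that 11.4 schedules after 50 patients per arm.

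Day 0 to 28 is preferable, because the two calls and the diary already cover it and it loses almost nothing to truncation. It is not the only sound choice: day 14 is acceptable if the diary score that makes a day restricted is defined. State whether day 0 counts.

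In 11.2, give the margin, SD and power for the chosen window. In 11.4, name the non-inferiority comparison, its arms and its one-sided level.

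The cost is wording and a power recalculation; no new visits or data are needed. The downside is that the SD over 28 days may exceed 4, in which case the stated power falls.
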